Secondary Outcome Measures. These measures represent underlying mechanisms that we hypothesize to be related to how the personalized interventions affect pain relief. These measures will be obtained at the same time each day (relative to the time of the initial shoulder injury) to avoid unwarranted variation.

Molecular: These measures will capture relevant inflammatory biomarkers. The low COMT activity of our high-risk group results in increased catecholamine activity, which augments release of proinflammatory cytokines under conditions of stress.⁹⁹⁻¹⁰¹ This catecholamine-evoked cytokine release can be attenuated by propranolol.⁹⁹⁻¹⁰² Moreover, catastrophizing, which also characterizes our high-risk group, has been associated with greater increases in circulating proinflammatory cytokines following both acute pain¹⁰³ and induction of pain-related negative emotions.¹⁰⁴ Thus, we hypothesize that personalized pharmaceutical or psychological intervention will significantly attenuate cytokine levels, with the greatest reduction observed in the combined personalized intervention condition. Moreover, because the increased pain evoked by COMT inhibition has been found to be mediated by increased circulating cytokines and reversed by blockade of beta-adrenergic (β 2 and β 3) receptors,⁷ we further expect that the attenuation of cytokine release will be associated with the efficacy of our combined personalized intervention for reducing pain and disability. Thus, we plan to perform assays for several inflammatory cytokines, including IL1B, IL6, IL8, and TNF α at baseline, immediately after the exercise-induced injury, and at regular intervals (Figure 5). All assays will be performed by the Metabolism and Translational Science Core of the Claude D. Pepper Older Americans Independence Center using commercially available kits with which they have extensive experience.

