Psychological: In addition to the aforementioned PCS, the Tampa Scale of Kinesiophobia which is an 11-item (TSK-11), 4 point rating scale to quantify avoidance and re-injury beliefs^{105, 106} and the Fear of Pain Questionnaire (FPQ-III) which is a 30-item, 5-point rating scale to quantify fear about specific situations that normally produce pain¹⁰⁷⁻¹⁰⁹ will be used to capture psychological processes. Consistent with a fear-avoidance model of musculoskeletal pain,¹¹⁰ we hypothesize that the personalized psychological intervention will reduce these levels significantly via cognitive restructuring providing subsequent decreases in disability and pain.

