
C4. Statistical Analysis Plan

All statistical analyses will be performed using the SAS software, version 9 (SAS Institute Inc, 1996). Summary statistics will be provided for baseline measures by intervention groups to determine if randomization produced balanced groups. Any group imbalance will be investigated further to determine if covariates should be considered. For Specific Aim #1, our primary analysis for efficacy will compare shoulder pain duration (i.e. *number of days until subject rated their current pain at 0/10 and their worst pain was rated less than 2/10*) across the four randomly assigned groups with the use of logistic regression. Consistent with the initial funding period, the primary outcome variable will be dichotomized based on duration of at least 7 days or not. There is an *a priori* plan to include age, sex, and race as covariates in this analysis, additional variables will be added as covariates only if imbalanced across groups and correlated with outcome measures. We anticipate very little missing data because this is a pre-clinical study, but any missing outcomes will be predicted by subject pain intensity trajectory plus baseline demographic factors. The primary comparison between the combined personalized intervention and the combined placebo condition will be tested at the 0.05 significance level, while the other five between group contrasts will be tested using a step-down procedure. For the other primary outcomes (peak pain intensity and upper-extremity disability as continuous measures) we will perform a similar analysis process (i.e. same considerations for post randomization imbalance, covariates, and missing data) with linear regression analysis to compare the four intervention groups. For Specific Aim #2, we will fit path models with predetermined orders to investigate the direct (intervention group) and indirect effects (through the mediating psychological, molecular, and pain sensitivity paths) of the randomly assigned condition on pain relief. The combined placebo intervention will serve as reference group for these analyses. The total, direct and indirect mechanistic effects on pain duration (dichotomous) and peak pain intensity and upper-extremity disability (continuous) will be estimated and tested at the 0.05 significance level for the comparison of assigned conditions. Specifically, the total effect will be estimated and tested through a logistic regression for pain duration and a general linear model for peak pain intensity, both of which include the assigned intervention conditions as independent variables while controlling for participant age, sex, and race. The direct effect will be estimated and tested with the use of the same models including the same independent variables, but controlling for mediating molecular, psychological, and pain sensitivity variables in addition to age, sex and race. The two regression models in the second step will reveal the contributions of the mediating psychological, molecular, and pain sensitivity variables on pain relief. On the other hand, the indirect effect will be calculated based on the difference between the total and direct effects. In addition, we will conduct a third

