
set of regression analyses to evaluate the effect of the assigned condition on the mediating variables which will determine which indirect paths are statistically significant.

C4. Sample Size Estimate and Study Timeline

A total of 448 high-risk subjects will be recruited. In the initial funding period we found that 40.5% of high risk subjects had pain duration \geq 7 days while 21.4% of the low risk group had long duration (Table 1). In our power analysis, we assumed that 40% of the combined placebo group will have long pain duration (rate for high risk subgroup), while the rate for the combined personalized intervention group will be 20% (rate for low risk group). Those with one personalized intervention were assumed to have 30% chance of having duration \geq 7 days. The planned sample size will enable us to have 80% power to detect the assumed differences across the four intervention groups and 91% power for the primary comparison between the combined personalized and the combined placebo interventions at a type-I error level of 0.05. The overall BISP timeline is in Table 3.

Table 3. Timeline and Key Periodic Events for BISP

Year 1		Year 2		Year 3		Year 4		Year 5					
Start Up	Quarterly Meetings with Research Team Annual Progress Reports to Institutional Review Board, Data Safety Monitoring Body, and NIH												
	Screening, Recruitment (annual rate = 96-120 participants), Intervention, and Follow Up												
	Scientific Conference		Scientific Conference		Scientific Conference		Scientific Conference		Scientific Conference				
On Site Consult		On Site Consult		On Site Consult		On Site Consult		On Site Consult	Analysis, Dissemination				

C5. Potential Pitfalls and Alternative Approaches

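### Aim 2: total minus direct from logistic models is not a valid indirect effect for dichotomised duration, and for every outcome the arm-to-mediator regression alone decides which indirect paths are significant

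*Combined protocol and SAP*

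**What the plan says.** C4 Statistical Analysis Plan describes three steps for Specific Aim #2, with combined placebo as the reference group.

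1. Total effect: "the total effect will be estimated and tested through a logistic regression for pain duration", and a general linear model for the continuous outcome, adjusted for age, sex and race.
2. Direct effect: the same models, "controlling for mediating molecular, psychological, and pain sensitivity variables in addition to age, sex and race". Of this step the plan says: "The two regression models in the second step will reveal the contributions of the mediating psychological, molecular, and pain sensitivity variables on pain relief". The indirect effect then follows by subtraction: "the indirect effect will be calculated based on the difference between the total and direct effects".
3. A third set of regressions, of the mediators on assigned condition, "which will determine which indirect paths are statistically significant".

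Total, direct and indirect effects "will be estimated and tested at the 0.05 significance level for the comparison of assigned conditions". The plan names no effect scale, no standard error or interval for the difference, and no product, joint or bootstrap test.

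C3, Secondary Outcome Measures, names at least ten mediators in three domains:
- Molecular: "assays for several inflammatory cytokines, including IL1B, IL6, IL8", plus TNF-alpha.
- Psychological: the PCS, the FPQ-III and the "Tampa Scale of Kinesiophobia which is an 11-item (TSK-11), 4 point rating scale".
- Pain sensitivity: suprathreshold heat pain, pressure pain threshold and conditioned pain modulation.

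**The concern.** There are two separate faults.

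**Duration only.** Adding a predictor of outcome to a logistic model moves the arm coefficient away from zero even if the arm has no effect on that predictor. Subtracting the two coefficients mixes this shift with any real mediation. The shift vanishes for rare outcomes, but C4 Sample Size Estimate assumes 40% and 20%. Because the direct-effect model controls for all three domains at once, small shifts from individually weak mediators add up.

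**All outcomes.** An indirect path needs two legs, arm to mediator and mediator to outcome. The second-step models estimate the second leg, but the plan does not make it part of the rule for calling a path significant. The third regressions contain no outcome, so read literally they return the same list of significant paths for duration, peak pain and disability.

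Aim 2 exists to say which mechanisms carry pain relief. For duration, the indirect effect, and any share mediated derived from it, can be distorted. For every outcome, a mediator that the intervention moves but that has no bearing on pain could be reported as a significant mechanism.

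**Working it through.** **The plan's own figures.** With 448/4 = 112 per arm (equal allocation assumed) and two-sided 0.05, power for 40% versus 20% is Phi{[0.20 x sqrt(112) - 1.96 x sqrt(2 x 0.30 x 0.70)] / sqrt(0.24 + 0.16)} = Phi(1.34) = 0.910, against the stated 91%. For 40/30/30/20% the 3-df noncentrality is 112 x 0.02/0.21 = 10.67, giving power 0.790, against the stated 80%. Both reproduce. They concern Aim 1, and the plan gives no power figure for Aim 2.

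**Assumptions.** The mediator is standard normal, with log odds ratio b per SD for long duration. The documents give no mediator effect sizes, so b is shown over a range. The comparison is combined placebo against combined personalized.

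**Duration, no mediation.** Total = logit(0.20) - logit(0.40) = -1.386 + 0.405 = -0.981. For each b, solve for the intercept a in each arm so that the average of expit(a + bM) over M ~ N(0,1) equals 0.40 (placebo) or 0.20 (combined), by Gauss-Hermite integration. Direct = a(combined) - a(placebo). The true indirect effect is zero. The last column comes from 800 simulated trials of 112 versus 112, with a percentile bootstrap interval (300 resamples) for total minus direct.

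| b per SD | Direct | Total minus direct | As % of total | Bootstrap interval excludes 0 |
|---|---|---|---|---|
| 0.25 | -0.993 | +0.012 | -1% | about 3% |
| 0.5 | -1.029 | +0.049 | -5% | about 11% |
| 1 | -1.160 | +0.179 | -18% | about 29% |
| 1.5 | -1.344 | +0.363 | -37% | about 55% |
| 2 | -1.561 | +0.580 | -59% | about 71% |

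Repeat simulations with 200 to 400 trials gave 27% to 35% at b = 1 and 48% to 53% at b = 1.5.

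**Ten mediators together.** The linear-predictor SD is b x sqrt(10 + 90 x rho). For b = 0.25 this is 0.79 (rho = 0) or 1.52 (rho = 0.3). The differences are +0.116 and +0.372, i.e. -12% and -38% of the total, with bootstrap rejection of about 27% and 51% (150 trials, 250 resamples). For b = 0.10 the range is -2% to -7%.

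**Duration, real mediation.** Shift the mediator mean in the combined arm towards benefit by s SD, keeping the marginal rates at 40% and 20%. The true share on the log-odds scale is [logit(0.20) - logit(p10)]/total, where p10 is the risk under the combined arm with the mediator distributed as under placebo. Example with s = 0.3 and b = 1: direct is -0.860, so total minus direct is -0.121 (12%); the natural indirect effect is -0.258 (26%).

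| b per SD | s = 0.3: difference method | s = 0.3: true | s = 0.8: difference method | s = 0.8: true |
|---|---|---|---|---|
| 0.25 | 6% | 8% | 19% | 20% |
| 0.5 | 10% | 15% | 36% | 39% |
| 1 | 12% | 26% | 63% | 69% |
| 1.5 | 9% | 34% | 85% | 90% |
| 2 | 2% | 39% | 104% | 102% |

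**Linear outcomes.** With the same subjects and covariates, total minus direct from least squares equals the product of the two legs, so the first fault does not reach peak pain or disability.

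**Path rule, all outcomes.** Let the arm move a mediator by d SD, with no mediator-outcome link. The third regression flags the path with probability Phi(d x sqrt(56) - 1.96). Requiring both legs at 0.05 multiplies this by 0.05.

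| d | Arm-to-mediator rule alone | Both legs |
|---|---|---|
| 0.2 | Phi(-0.46) = 32% | 1.6% |
| 0.3 | Phi(0.28) = 61% | 3.1% |
| 0.4 | Phi(1.03) = 85% | 4.2% |
| 0.5 | Phi(1.78) = 96% | 4.8% |

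A simulation with a continuous outcome (4,000 trials) gave 62% and 96% at d = 0.3 and 0.5 for the rule alone, and 2.9% and 4.9% with both legs required.

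**The case against.** **Direction.** The false rejections for duration run against the claimed benefit. In a 400-trial run over the same five strengths, intervals excluded zero on the opposite-sign side in 4%, 13%, 27%, 53% and 71% of trials, and on the pain-relief side in at most 0.75%. This stands: for duration the difference seldom invents a pain-relief mechanism. It hides mediation or suggests suppression, which is still a wrong answer to Aim 2.

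**Size.** Large errors need strong mediators. A log odds ratio of 1.5 or 2 per SD implies a latent R-squared of about 41% or 55%, and the correlated ten-mediator case also reaches about 41%. The nearest anchor, Table 1 (40.5% versus 21.4%), is a log odds ratio of 0.92, or about 0.39 per SD of the risk indicator; one mediator of that strength gives about -3%. This also stands, but it is a baseline marker. The mediators are post-injury measures, at least ten enter together, and C3 says the pain sensitivity measures were chosen partly because an association with pain relief was expected.

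**Reading.** The plan promises a 0.05 test of indirect effects and estimates both legs, so one could assume they will be combined sensibly. But no combining rule is written, and the one sentence on path significance gives the decision to the third regressions. The difference from a model holding all mediators is a single joint effect, so it cannot settle individual paths. It is fair that the 32% to 96% depend on the literal reading and on no mediator-outcome link.

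**Scale and assumptions.** A difference in standardised risks would avoid the first fault, but the plan does not specify one. The linear difference method also needs no mediator-outcome confounding and no arm-by-mediator interaction, so those assumptions should be stated for every outcome.

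**Conclusion.** The concern holds, and both rules give wrong results if followed as written.

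For duration, on the log-odds scale, the bias is negligible for one weak mediator and small when the arm shift is large. It becomes material when mediators predict duration strongly or many enter together: a spurious 18% of the total effect at a log odds ratio of 1 per SD, 12% to 38% for ten mediators at 0.25 each, and 12% estimated against 26% true for a 0.3 SD shift at a log odds ratio of 1. A 0.05 test of this difference does not hold its level unless the mediators are weak.

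For all outcomes, the path rule omits the mediator-outcome leg.

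These sizes rest on assumed mediator strengths, normal mediators, equal allocation and no covariates. Aim 1 and its 91% power are untouched. This should be fixed before analysis.

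**What to change.** - **Duration:** replace the coefficient difference with a natural indirect effect computed from the fitted outcome and mediator models, for example on the risk-difference scale, or with a rescaled or product estimator. Use bootstrap intervals.
- **Order:** estimate the effect first for all mediators jointly, then by domain in the predetermined order the plan mentions, and write that order out.
- **Assumptions:** state that the decomposition requires no unmeasured mediator-outcome confounding.
- **All outcomes:** call an indirect path significant only if the interval for that indirect effect excludes zero or both legs are significant. Delete the statement that the third set of regressions determines path significance.
- **Peak pain and disability:** keep the difference method.

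The duration fix was checked by simulation with no mediation (log odds ratio 0.5 to 2, 500 trials each). The risk-difference natural indirect effect averaged within 0.002 of zero, and its bootstrap test rejected in 4.6% to 6.2% of trials with one mediator and 2% to 3% with ten.

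The cost is SAP wording and some extra programming, with no new data or participants.
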